NEPTUNELink has been designed to prevent unauthorized access to data and to prevent data loss due to equipment failure or catastrophic events. Security procedures encompass user account management, user privilege assignment, data loss prevention (database backup), computer systems validation, and performance monitoring. User access is controlled by assignment of confidential usernames, passwords, and role assignment. The databases are hosted on secure Arbor Research computing servers and are restricted to only those individuals who are authorized to work on the study. Additional measures to prevent unauthorized external access to the database environment are employed using network firewall technologies. Arbor Research provides for daily protection against data loss through high speed, high capacity disk drives that are used to create disk to disk copies and simultaneous disk to tape copies of the data. The DACC and Arbor Research has Standard Operating Procedures established for authorizing and

documenting secure access to the study website, documents and NEPTUNELink. These procedures ensure that only authorized personnel are able to view, access and modify study data.

6.C.3. Standard Reports

In order to evaluate enrollment, the DACC will use the real-time study management capabilities of NEPTUNELink to generate monthly reports that described overall study accrual by site and demographic characteristics of the population.

On a quarterly basis, the DACC will generate reports that represent the study data collected as well as assessment of that data. The following list represents data and quality reports:

- Study accrual: overall, by site, compared to target
- Demographic characteristics of the population
- Participants screened versus enrolled
- Reasons for screening failure
- Enrollment and withdrawal reports
- Contact completion rates [Follow-up visits expected v. completed]
- Timely data entry reports

6.C.4. Data Safety Management Plan

The study protocol will be reviewed and approved by the National Institutes of Health (NIH) before submission to individual center IRB's for approval. Participant enrollment may only begin with IRB approved consent forms.

This is an observational study that meets the federal definition of minimal risk.

6.C.5. Study Oversight

The Study PI has primary oversight responsibility of this observational study. The NIH appointed Data/Observational Safety Monitoring Board (D/OSMB) has oversight responsibility of the Data Safety Monitoring Plan (DSMP) for this clinical trial. The D/OSMB will review accrual, patterns and frequencies of all adverse events, protocol compliance every 12 months. The D/OSMB makes recommendations to the NIH regarding the continuation status of the protocol.

Each site's Primary Investigator and their research team (co-Investigators, research nurses, clinical trial coordinators, and data managers) are responsible for identifying adverse events. Aggregate report- detailed by severity, attribution (expected or unexpected), and relationship to the study procedures – will be available from the DMCC for site review. Adverse events will be reviewed no less than quarterly by the research team. The research team will then evaluate whether the protocol or informed consent document requires revision based on the reports.

6.C.5.a. Definitions and Standards

- The Rare Diseases Clinical Research Network defines an adverse event as: "...an unfavorable and unintended sign, symptom or disease associated with a participant's participation in a Rare Diseases Clinical Research Network study."
- Serious adverse events include those events that: "result in death; are life-threatening; require inpatient hospitalization or prolongation of existing hospitalization; create persistent or significant disability/incapacity, or a congenital anomaly/birth defects."
- Unexpected adverse events are defined as any adverse experience(s)...the specificity or severity of which is not consistent with the risks of information described in the protocol.
- Expected adverse events are those that are identified in the research protocol as having been previously associated with or having the potential to arise as a consequence of participation in the study

- All reported adverse events will be classified using the current version of the Common Terminology Criteria for Adverse Events (CTCAE) developed and maintained by CTEP at National Cancer Institute.
- For observational studies: Only those events associated with the conduct of the study and as defined above are reportable.

6.C.5.b. Adverse Events

Expected/Known Risks/Discomforts/Adverse Events Associated with Study Intervention and Procedures: Definition of Expected Adverse Events

Study Procedures:

- Venipuncture: Drawing blood causes discomfort when the hand or arm is stuck with the needle. A bruise may appear for a few days at the spot where the hand is stuck. There is a slight chance of infection. This is very unlikely. These risks are minimized by the use of trained personnel to draw blood. There is risk associated with light-headedness, dizziness and rarely fainting associated with blood draws.
- Kidney biopsy: When having a kidney biopsy for regular medical care, providing an additional core to the BioBank adds minimal risk to this procedure based on our review of the current literature. Participants' physicians will provide a separate consent. Participants' physicians will explain the reasons for a clinical biopsy. After all the studies needed for clinical care are finished, surplus samples will go to the NEPTUNE BioBank.

6.C.5.c. Reporting Timeline

Within 24 hours (of learning of the event), investigators must report any reportable Serious Adverse Event (SAE) that:

- Is considered life-threatening/disabling or results in death of subject
- OR-
- Is Unexpected/Unanticipated
- Investigators must report all other reportable SAEs within 5 working days (of learning of the event).
- All other (suspected) reportable AEs must be reported to the RDCRN within 20 working days of the notification of the event or of the site becoming aware of the event.
- Local institutional reporting requirements to IRBs, any GCRC oversight committee and the FDA, if appropriate, remain the responsibility of the treating physician and the Study PI.

6.C.6. RDCRN Adverse Event Data Management System (AEDAMS)

Upon entry of a serious adverse event into the NEPTUNELink system, the Study PI, site PIs, the Medical Review Officer, and NIDDK program officer will be immediately notified via email. This data will then be electronically transferred to the DMCC created Adverse Event Data Management System (AEDAMS).

Serious adverse events: The NIH appointed Medical Review Officer (MRO) will review causality (definitely not related, probably not related, possibly related, probably related, definitely related) of the adverse event. The MRO may request further information if necessary and possibly request changes to the protocol or consent form as a consequence of the adverse event. A back-up notification system is in place so that any delays in review by the MRO beyond a specified period of time are forwarded to a secondary reviewer. The Adverse Event Data Management System (AEDAMS) maintains audit trails and stores data (and data updated) and communication related to any adverse event in the study.

Non-serious expected adverse events: Except those listed above as immediately reportable, non-serious expected adverse events that are reported to or observed by the investigator or a member of his research team will be submitted to the DMCC in a timely fashion (within 20 working days). The events will be

presented in tabular form and given to the MRO and RDCRN DSMB on an annual basis. Local site investigators are also required to fulfill all reporting requirements of their local institutions.

The DMCC will post aggregate reports of all adverse events (serious/not serious and expected, unexpected) for site investigators and IRBs.

6.C.7. Study Discontinuation (Observational)

This study will not have study discontinuation rules as it is an observational study. The NIH and local IRB's have the authority to stop or suspend this trial at any time.

6.C.8. Subject Discontinuation

As an observational study, continued monitoring of every enrolled and eligible subject is anticipated unless withdrawal is requested for the indications listed below. All data acquired prior to termination for the reasons outlined below will be included in the primary analysis unless patient withdraws consent. Every effort will be made to conduct a final study visit with the participant and participants will be followed clinically until, if applicable, all adverse events resolve.

Withdrawal of consent

Withdrawal by the participant

Withdrawal by the investigator

Intercurrent illness or event that precludes further visits to the study site or ability to evaluate disease (e.g.-mental status change).

NIH Approved 03/29/2019

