Data Sources: The NEPTUNE study participant contact pattern includes study visits and interim phone calls on an as-needed basis. For selected sites that have access to electronic administrative or billing records, regular searches of those data sources will be performed (e.g., quarterly) for their center's study participants. We will also explore the feasibility of using additional databases (National Death Index, USRDS and SRTR) to identify outcomes, although it is clearly recognized that there is often a long delay (e.g., 12-18 months or longer) in getting access to these files, which are updated annually and require additional governmental approval. In preparation for use of national data sources, the patients will be consented for the collection of the social security number for use in assessing vital status, ESRD status and transplant status using these national data sources.

Outcome Search Strategy: For potential clinical events that lead to hospitalization, we will acquire information from the study participant or their self-assigned proxy regarding the dates (admission and discharge) and hospital (name, address, phone number) where the patient was hospitalized. The scope of medical record acquisition is limited to the following events: hospitalizations, infectious episode requiring parenteral antibiotic therapy, outpatient cardiac catheterization, outpatient ECHO (MUGA or nuclear perfusion imaging), new onset heart failure, extended (>24 hour) ER or observation unit stay.

For potential clinical events that do not lead to hospitalization, we will acquire information from the study participant or their self-assigned proxy regarding the date of the potential event

and the location where the patient received treatment (e.g., outpatient clinic/surgicenter, address, phone number, and treating physician).

Patient Reported Information using SMS (text messaging): Participants in the cNEPTUNE cohort will report results of home urine protein testing, edema status, medication adherence, presence of infections, stressors, or allergies, and work and school absences. Tailored text messages will be sent to the designated parent/patient throughout the initial year of study participation.

3.E.3. Intra-renal Gene Expression Exposure Variables

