- Pharmaceutical companies will be solicited through their patient assistance program for bulk supply of medications commonly prescribed to patients with kidney disease including antihypertensive, anti-lipid and antidiabetic drugs. These medications will be distributed by the DACC to the participating clinical centers for the use of study participants who need such assistance. We found this measure to be helpful in maintaining retention for other clinical studies.
- Participant reimbursement initially set at \$100 will be supplemented with an additional mileage reimbursement for participants traveling more than 100 miles to the clinical center for study visits.
- Per diem expenses for overnight accommodation will be provided to study participants whose travel calls for this, particularly during seasons of inclement weather.
- Participating clinical centers will be encouraged to offer evening and weekend appointments to make it possible for participants with work and other obligations that limit their flexibility to attend study visits during regular business hours (8:00 AM – 5:00 PM Monday-Friday).
- Mailing of appointment reminders, formal study participation anniversary greetings, newsletters and intermittent courtesy calls, courtesy visits to the participants during hospitalization and recognition of major life events are additional measures that will be undertaken to embrace study participants and hopefully retain their participation.
- Participants for whom relocation brings about a change of providers and an excessive travel burden for completion of study visits may continue in the study by completing phone call visits, on a case-by-case basis with permission from the DACC. In such instances, biological specimens and processing will be coordinated with a local laboratory and shipped directly to the NEPTUNE Biorepository.
- Discomfort that can result from study procedures will be rigorously minimized. For example, many of the participants may be on immunosuppressants with myelosuppressive adverse effect as part of the treatment for FSGS leading to high risk of anemia. Therefore, phlebotomy for study purposes will not withdraw more than 250 cc annually. Adult participants with hematocrit <28% will follow the pediatric volumes at that particular study visit (see Manual of Procedures for pediatric blood draw reductions). Participants with hematocrit <25% will have study phlebotomy waived for that particular study visit.

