Retention of participants is central to the internal validity of the study and will be an extraordinarily high priority of the investigators and staff. A key element is a pleasant, attentive and responsive staff that provides a reasonably flexible visit schedule. Other clinical center features that promote high retention rates include local tracking systems; frequent staff meetings; free and convenient parking; personal contacts through birthday cards, holiday cards, sympathy cards and flowers; small gifts at visits; and modest monetary incentives.

There exist limited research data on participant retention in non-therapeutic clinical studies similar to the proposed cohort studies. Lack of therapeutic interventions may heighten the perception of no benefit in participation on the part of the study participant. The study team is acutely sensitive to this issue and would continue to evaluate new retention methods that can be tested and implemented in the cohort studies. The aggressive retention measures that are proposed herein will, in practice and in principle, always give way to the welfare of the study participants who are, first and foremost, patients. Respect, care and empathy for the circumstances of the participants will be the overriding consideration in all aspects of the recruitment and retention plan laid out by the proposing team.

4.C. Participant Withdrawal

It is anticipated that over the course of time, participants may withdraw from the study. This may occur officially by formal notification from the participant to the investigator, or unofficially when a participant cannot be reached via the usual methods of contact. Every effort will be made to acquire complete data on all participants.

As a longitudinal, observational study, missed study visits and unanticipated loss of contact are not deemed dangerous to the study participants.

Participants who relocate to an area from which it is no longer feasible to travel to the clinical center will be asked to permit study personnel to contact them annually for a telephone contact follow-up. Centers may offer inducements to participants who drop-out or relocate in the form of additional travel reimbursement in return for their continued participation. A participant relocating to an area close to a different NEPTUNE clinical center may transfer to that center.

4.D. Clinical Management of Participants

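### Section 6.C.8 makes illness that prevents site visits a stand-alone ground for ending participation and names no remote follow-up, so loss of follow-up is plausibly related to outcome

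*Protocol*

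**What the plan says.** Section 6.C.8 (Subject Discontinuation) starts from the position that "continued monitoring of every enrolled and eligible subject is anticipated unless withdrawal is requested for the indications listed below". Four grounds follow: withdrawal of consent, withdrawal by the participant, withdrawal by the investigator, and "Intercurrent illness or event that precludes further visits to the study site or ability to evaluate disease (e.g.-mental status change".

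On data, the section says "All data acquired prior to termination for the reasons outlined below will be included in the primary analysis unless patient withdraws consent". On contact, it says "Every effort will be made to conduct a final study visit with the participant", with clinical follow-up until any adverse events resolve. It names nothing further.

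Participants who cannot attend because they moved are treated differently:

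- **4.B:** those whose move makes travel excessive "may continue in the study by completing phone call visits, on a case-by-case basis with permission from the DACC", and for them "biological specimens and processing will be coordinated with a local laboratory".
- **4.C:** those who move out of reach are asked to allow an annual telephone contact. The same section states the general aim: "Every effort will be made to acquire complete data on all participants".

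Several means of collecting data without attendance are already in the protocol, but none is tied to 6.C.8:

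- **3.E.2.a:** for events leading to hospitalization, "we will acquire information from the study participant or their self-assigned proxy regarding the dates (admission and discharge) and hospital".
- **3.C.2 and 3.D.1 (follow-up visits):** local laboratory results and electronic-record updates are entered on the forms of a missed visit.
- **3.C.1:** renal function measured for clinical purposes between visits may enter the database.
- **3.E.2.a and 6.C.1:** social security numbers are collected for vital, ESRD and transplant status, and sites may link to registries.

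**The concern.** A cohort study needs the reason for leaving follow-up to be unrelated to what would have been observed next. Being too ill to travel is a reason that plausibly is related. Malignancy, serious infection, thromboembolic events and death are listed secondary outcomes (3.E.2). The first three are also plausible causes of being unable to attend.

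The justification of the renal outcome in 3.E.1.b relies on censoring participants who depart early, and 3.F.5.e applies Cox regression to the primary and secondary endpoints. Both assume that a censored participant has the same prospects as those who remain. If participants are censored because they are seriously ill, adverse event rates are likely to be underestimated. Remission would be overestimated if those participants are less likely to remit.

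The contrast with relocation makes this avoidable. The protocol accepts remote data when the obstacle is distance, but names no such route when it is illness.

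**Working it through.** **1. Is illness a separate ground?** Withdrawal of consent, by the participant and by the investigator are already on the list. The illness item therefore adds something: inability to attend, or to have disease evaluated. A site may reasonably apply it as written.

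**2. Which outcomes are lost?**

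| Outcome | Route without attendance | Firm after an illness termination? |
|---|---|---|
| 25 ml/min/1.73m² or 50% eGFR decline (3.E.1) | Local creatinine, missed-visit forms | No: described for participants still in follow-up, not linked to 6.C.8 |
| Proteinuria remission (3.E.1.a) | Local urine results, missed-visit forms | No: same reason |
| ESRD | Registry linkage; 3.E.1.b says the time can be found after study completion | Conditional |
| Death | National Death Index | Conditional |

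The linkage is conditional because 3.E.2.a commits only to exploring whether registries can be used and warns of delays of 12-18 months or longer. Section 6.C.1 leaves linkage optional for sites. Linkage for vital, ESRD and transplant status would not supply serial creatinine or urine protein, so the laboratory-based loss is the firmer one.

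**3. The plan's own attrition figure.** Section 4.B requires retention above 85% and ties this to an average annual loss of at most 5%. Over the 36-month minimum follow-up:

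- compound: (1 − 0.05)³ = 0.857
- linear: 1 − 3 × 0.05 = 0.85

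The figure reproduces. It limits how many participants are lost, not which ones.

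**4. Illustration of size.** The following are assumptions, not figures from the protocol: a constant hazard, a true 36-month risk R of the event, and a share f of events preceded by an illness termination. Censoring falls just before the event and nothing is ascertained later. The estimated risk is then

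1 − (1 − R)^(1 − f).

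For R = 10% and f = 25%: 1 − 0.90^0.75 = 7.60%.

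| R | f = 10% | f = 25% | f = 50% |
|---|---|---|---|
| 5% | 4.51% | 3.77% | 2.53% |
| 10% | 9.05% | 7.60% | 5.13% |
| 15% | 13.61% | 11.48% | 7.80% |

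The relative shortfall is about 9-10%, 24% and 48-49% for the three values of f, whatever the cohort size. With N = 250 + 200 = 450 (3.F.2), the case R = 10%, f = 25% misses 450 × (0.100 − 0.076) ≈ 11 events.

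In that case the terminations that precede an event affect only R × f = 2.5% of participants over three years, against an allowance of about 15%. Meeting the retention target therefore gives no protection.

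**5. Effect of linkage.** If linkage is done and captures death and ESRD, the shortfall for those two outcomes falls towards zero. It does not for eGFR decline or remission.

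**The case against.** A reader might infer that participants too ill to attend are automatically dropped, that those who move are always kept, and that follow-up therefore stops just before death and ESRD. The documents do not support that reading:

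- Section 6.C.8 speaks of withdrawal being requested, and the illness must preclude further visits or evaluation. A stroke or sepsis does not do so by itself.
- Relocated participants stay only case by case with the coordinating center's permission, or if they agree to calls. Chart extraction is not a relocation provision: 3.C.2 describes it for visits from V9 onward.
- Death and ESRD are the outcomes with the best off-site provision, though it is conditional. Timing just before them is an inference.
- The effect on Aim 7 is limited. Its composite covers vascular thrombosis, biopsy complications, infection and death, so a participant with an embolic stroke or sepsis has probably already counted before any termination. On a first-event reading, a later death adds nothing.
- The direction of bias is clear only for absolute risks. For covariate associations and the prediction model, the primary analysis in 3.F.4, it is not determined.
- Analyses for informative censoring may stand in a statistical analysis plan that is not at hand, so their absence is no finding.

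All of this stands and limits the claim. It does not remove the gap: illness is a separate ground, no remote route is named for it, and the general aim of complete data in 4.C gives no method for these participants. An analysis plan can examine the effect of missing follow-up, but it cannot supply creatinine, urine protein or vital status that was never collected.

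**Conclusion.** The point holds in a limited form. Section 6.C.8 permits participation to end because of illness without remote follow-up, while participants who relocate have named, if conditional, substitutes. Loss of follow-up is then plausibly related to outcome. This is most certain for eGFR decline and proteinuria, and extends to death and ESRD only if linkage is not carried out.

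The size cannot be computed from the documents, because they give no rate of illness termination. The illustrated shortfalls, from about 9% to 49% of the true risk, rest wholly on assumed values of R and f and on no later ascertainment. They show the mechanism and are not an estimate for this study.

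This is a cheap improvement, not a flaw that undermines the design.

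**What to change.** In 6.C.8, remove inability to attend because of illness as a ground for discontinuation. State instead that such participants move to remote follow-up, consisting of:

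- local laboratory values (creatinine, urine protein) and chart or electronic-record abstraction at each scheduled visit;
- contact with the self-assigned proxy;
- linkage for death and ESRD where consented.

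Remote follow-up ends only on withdrawal of consent, by the participant or a legally authorized representative, or on withdrawal by the investigator. The representative needs naming because the protocol's own example is a change in mental status, where the participant may be unable to give or refuse permission.

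Then reconcile 6.C.8 with the missed-visit rule in 3.C.2, the statements on censoring and later ESRD ascertainment in 3.E.1.b, the data sources in 3.E.2.a, the relocation provisions in 4.B and 4.C, and the linkage option in 6.C.1.

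The cost is a paragraph of wording with cross-references, some chart abstraction, and local instead of central laboratory values for a few participants. No new data system is needed.
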